While the possibility of ADE from administration of high dose conventional IVIG cannot be entirely ruled out. The available data from the earlier SARS epidemic, and currently early case series of COVID-19 from China suggest that the over-riding effect of high dose IVIG (2 g/kg) is immunomodulatory and salutary in cases where the immune inflammatory response may be producing harmful collateral damage. Therefore, the premise of the current study is that high dose IVIG (2 g/kg total in divided doses) may produce therapeutic benefit for serious COVID-19 requiring hospitalization and ICU admission; the aim is to intervene and modulate the inflammatory cascade in order to reduce mortality.

2.4 Description of and Justification for the Route of Administration, Dosage, Dosage Regimen, and Treatment Periods

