8.5 Study-Independent Safety Review Committee (SISRC) and Stopping Rules

Grifols will utilize a Study-Independent Safety Review Committee (SISRC) whose members (from Grifols) will be impartial and independent of the clinical trial team, and will consist of a statistician, global pharmacovigilance representative, and medical director. The SISRC will review relevant safety information from the study as outlined in the SISRC Charter. At a minimum, after the first 20 subjects are enrolled and have completed treatment, the SISRC will conduct an initial safety review. The SISRC will perform a causality review of all TEAEs and SAEs. The SISRC will be notified of relevant SAEs inasmuch as feasible within 24 hours, but no later than 3 days.

Stopping criteria for temporary suspension of further study enrollment/recruitment pending full safety investigation by the SISRC are detailed below.

The SISRC will conduct a safety evaluation and study enrollment/recruitment will be temporarily suspended while the safety investigation is undertaken if any one of the following occur:

- 1 death considered related to Gamunex-C
- 1 Grade 4 treatment-emergent AE occurs in any of the first 3 randomized subjects considered potentially related to Gamunex-C
- 1 subject develops a Grade 3 hypersensitivity reaction or serious anaphylactic reaction at any time attributable to Gamunex-C
- 10 subjects given Gamunex-C develop treatment-emergent AEs in the same system organ class that are \geq Grade 2 severity (CTCAE grading criteria)
- 2 subjects given Gamunex-C develop treatment-emergent Grade 4 serious AEs of the same kind in the first 10 subjects randomized to Gamunex-C
- 5 subjects develop Grade 3 or 4 treatment-emergent AEs that are at least possibly related to Gamunex-C at any time during the study
- 3 or more subjects per 10 subjects enrolled and dosed with Gamunex-C develop definitely related treatment-emergent serious AEs of the same kind (same or related verbatim terms). This stopping criterion will be applied after at least 10 subjects are randomized and treated with Gamunex-C.

GRIFOLS	Number	BLG-CL-PPR-000020	Version	4.0	Status	Effective	Effective Date	19-Jul-2021
	GC2007 - A Multicenter, Randomized, Open-label Parallel Group Pilot Study to Evaluate Safety and Efficacy of High Dose Intravenous Immune Globulin (IVIG) plus Standard Medical Treatment (SMT) versus SMT alone in Bioscience Industrial Group						Page	63 of 91

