- An unanticipated safety signal is detected by the SISRC that was unexpected and of sufficient magnitude to warrant concern

Further details are outlined in the SISRC Charter.

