### **8. INTERIM ANALYSES**

An interim analysis will be conducted after 50 subjects (approximately 25 per group) for safety variables through Day 29. Due to the exploratory nature of this phase 2 study, the multiplicity adjustments will not be considered. This interim evaluation simply represents Sponsor safety due diligence. This interim analysis will analyze safety variables including, but not limited to, the following: adverse events (see Section 7.2), clinical laboratory parameters (see Section 7.3), and vital signs (see Section 7.4). The relevant methods described in Section 7 (Safety Analysis) of this SAP intended for the final analysis will also be applicable to the interim analysis.

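### The same-kind serious-event pausing rule names Grade 4 only, so two fatal events judged unrelated do not count where two survived ones would suspend enrolment

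*Protocol*

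**What the plan says.** Protocol 8.5 lists eight criteria. Any one of them suspends enrolment while the Study-Independent Safety Review Committee (SISRC) investigates. The fifth reads "2 subjects given Gamunex-C develop treatment-emergent Grade 4 serious AEs of the same kind in the first 10 subjects randomized to Gamunex-C". It has no causality wording.

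The only criterion that names death is "1 death considered related to Gamunex-C". Another is "5 subjects develop Grade 3 or 4 treatment-emergent AEs that are at least possibly related to Gamunex-C at any time during the study". The system-organ-class criterion applies when "10 subjects given Gamunex-C develop treatment-emergent AEs in the same system organ class that are" of Grade 2 or higher, with no upper limit. The last is discretionary: "An unanticipated safety signal is detected by the SISRC that was unexpected and of sufficient magnitude to warrant concern".

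Protocol 8.3.5 divides severe events into Grades 3 to 5 on the CTCAE scale, and 8.3.8 records severity up to Grade 5. The protocol does not print the grade definitions; Grade 5 is taken here as the fatal grade of that scale.

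For the interim after 50 subjects, SAP 8 says "This interim analysis will analyze safety variables including, but not limited to, the following: adverse events", followed by laboratory values and vital signs, and carries over the methods of SAP 7. SAP 7.2.5 tabulates treatment-emergent adverse events (TEAEs) leading to death, whatever their relationship to the product. All-cause mortality is analysed under efficacy (SAP 6.1) and is not named for the interim.

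**The concern.** A worse outcome counts for less than a milder one. The same list sets a floor without a ceiling in the system-organ-class rule, so the open-ended form was available. Nothing in the documents suggests that leaving fatal events out of the same-kind rule was intended.

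Two other rules also stop at Grade 4, but little is lost there. They apply only to events attributed to Gamunex-C, and one related death triggers a pause by itself. The same-kind rule is different because it works without attribution, and no equivalent rule picks up a fatal event judged unrelated.

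Attribution is a weak filter in an open-label trial in ICU patients with COVID-19. Protocol 2.3.2 and 8.3.1 name thromboembolism as an IVIG risk, while a fatal pulmonary embolism in such a patient can readily be put down to the disease. At stake is whether an early cluster of fatal events of one kind leads to an automatic pause or depends on someone choosing to act.

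**Working it through.** **Step 1. Apply the eight criteria to one case.** Two of the first 10 IVIG subjects have a fatal event of the same kind, judged unrelated.

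| Criterion (Protocol 8.5) | Causality required | Grades | Do the two events count? |
|---|---|---|---|
| 1 death | related | fatal | no |
| 1 event in the first 3 randomised | potentially related | 4 | no |
| Hypersensitivity or anaphylaxis | attributable | 3, or serious | no |
| 10 IVIG subjects in one system organ class | none | 2 and above | yes, as 2 of the 10 needed |
| 2 of the first 10 IVIG subjects, same kind | none | 4 | no |
| 5 subjects | at least possibly related | 3 or 4 | no |
| 3 or more per 10 dosed, same kind | definitely related | any serious | no |
| Unanticipated signal | none | none stated | at SISRC discretion |

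If the same two subjects survive with Grade 4 serious events, the fifth criterion is met and enrolment stops for review. The signal rule is worded for unanticipated, unexpected findings, and a risk that the protocol already names arguably falls outside it.

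**Step 2. Size of the gap.** The plan states no operating characteristics and no event rates, so there is no figure to reproduce and every rate below is an assumption. Let p4 and p5 be the proportions of IVIG subjects whose worst event of one kind is Grade 4 or Grade 5, with subjects independent. With n = 10:

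P(X ≥ 2) = 1 − (1 − p)^10 − 10·p·(1 − p)^9, with p = p4 as written and p = p4 + p5 if Grade 5 counts.

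- As written, p = 0.10: 1 − 0.349 − 0.387 = 0.264.
- With Grade 5, p = 0.20: 1 − 0.107 − 0.268 = 0.624.

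| Assumed p4 | Assumed p5 | As written | Grade 4 or 5 |
|---|---|---|---|
| 5% | 10% | 0.086 | 0.456 |
| 10% | 10% | 0.264 | 0.624 |
| 10% | 20% | 0.264 | 0.851 |
| 20% | 10% | 0.624 | 0.851 |
| 20% | 20% | 0.624 | 0.954 |

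As written, the trigger probability does not change with the fatal rate.

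**Step 3. Does the system-organ-class rule fill the gap?** Among the first 10 IVIG subjects, all 10 would have to be affected. The probability of at least 10 affected subjects is:

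| IVIG subjects | Assumed rate 20% | 30% | 40% |
|---|---|---|---|
| 25 | 0.017 | 0.189 | 0.575 |
| 50 | 0.556 | 0.960 | 0.999 |

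It is slow at the point where the 2-of-10 rule is meant to act.

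**Step 4. Deaths at the interim.** SAP 8 points to SAP 7.2.5, which tabulates TEAEs leading to death. SAP 4 provides summaries for each treatment group. SAP 4.2 bases them on the Safety population by treatment received, which leaves out subjects randomised to IVIG but never infused. Protocol 8.3.3.1 keeps COVID-19 symptoms from being recorded as individual TEAEs unless a causal link to IVIG is suspected. On the other side, death is a seriousness criterion (8.3.7), and serious events are reported whatever their attribution (8.3.9). The documents do not say outright whether a death from disease progression is entered as a fatal TEAE.

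**The case against.** **The SISRC sees fatal events anyway.** It is told of relevant serious events within 3 days at most and reviews causality for all TEAEs and serious events. The sponsor also makes its own causality assessment (Protocol 8.3.4), so an investigator's judgement of unrelated is not final. The SISRC Charter, which is not among the documents, may say more. This stands: the gap is in the automatic trigger, and does not mean that nobody looks.

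**Requiring relatedness for deaths is defensible in an ICU.** The rule has no control comparison. If mortality were 20% to 40% (assumed) and every death were coded as one kind, at least 2 of the first 10 would die with probability 0.62 to 0.95 with no IVIG effect at all. That is an upper bound, because the rule needs events of the same kind. It stands as a cost, and it means that the higher trigger probabilities in the working do not by themselves show better detection of harm.

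**A stronger reading is tempting.** The protocol concedes of antibody-dependent enhancement (ADE): "While the possibility of ADE from administration of high dose conventional IVIG cannot be entirely ruled out". A reader might infer that excess IVIG deaths of this sort, looking like worse COVID-19, would go unnoticed at the interim. The documents do not support that. The SAP 8 list is open, and it leads to fatal TEAEs by treatment group with no causality filter. The recording restriction covers symptoms and does not exempt deaths. What remains is an ambiguity about disease-progression deaths. Adding Grade 5 to the same-kind rule would not resolve it, because a death with no TEAE would still not count there.

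**A reader might also want the Ordinal scale by arm.** That is a secondary efficacy endpoint, the interim is limited to safety, and the SISRC consists of sponsor staff. Its 20-subject review follows completion of treatment, when some Day 15 and Day 29 values may not yet exist. The point does not need it.

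**Conclusion.** The main point holds on the text. The only same-kind serious-event rule free of a causality judgement names Grade 4 and omits Grade 5, and no other numeric rule promptly covers two early fatal events judged unrelated. If 20% of IVIG subjects had a Grade 4 or 5 event of one kind, half of them fatal, the rule would fire with probability 0.26 instead of 0.62. These figures rest on assumed rates, independence between subjects, and fatal events being judged unrelated.

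The secondary point is narrower. No pausing rule counts all-cause deaths by arm, and the interim names deaths by arm only as TEAEs leading to death in the Safety population. Whether that equals all deaths depends on a recording convention that the documents leave unstated. This is a call for clarification; it does not show that deaths would be missed.

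**What to change.** 1. In the fifth criterion of Protocol 8.5, change Grade 4 serious AEs to Grade 4 or 5 serious AEs. This takes two added words. The cost is that enrolment may be temporarily suspended for review more often because of background ICU deaths. A trigger leads to a pause and a review, not to a change in any subject's care.

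2. In SAP 8, state that the interim safety output includes a count of every death by arm, including deaths from disease progression and deaths among randomised subjects who were never infused, with no efficacy test. The vital-status data are already collected. The cost is one descriptive table that shows the primary endpoint by arm to sponsor staff during an open-label trial; the planned table of fatal TEAEs by arm already shows much of this.

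### The 3-per-10 same-kind related-SAE suspension rule in Protocol 8.5 is held back until 10 subjects are dosed, even when its threshold has already been reached

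*Protocol*

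**What the plan says.** Protocol 8.5 lists eight triggers. On any one of them, "study enrollment/recruitment will be temporarily suspended while the safety investigation is undertaken if any one of the following occur". The trigger at issue is "3 or more subjects per 10 subjects enrolled and dosed with Gamunex-C develop definitely related treatment-emergent serious AEs of the same kind", meaning the same or related verbatim terms. It is followed by "This stopping criterion will be applied after at least 10 subjects are randomized and treated with Gamunex-C".

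The other numeric triggers carry no such wait:

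- a single death judged related to the product
- one potentially related Grade 4 TEAE among the first 3 randomized
- one Grade 3 hypersensitivity or serious anaphylactic reaction attributed to the product
- for Grade 4 events of one kind: "2 subjects given Gamunex-C develop treatment-emergent Grade 4 serious AEs of the same kind in the first 10 subjects randomized to Gamunex-C"
- five subjects, at any time, with Grade 3 or 4 TEAEs judged possibly or definitely related
- ten Gamunex-C subjects with TEAEs of Grade 2 or higher in one system organ class.

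The eighth trigger is a signal that the Study-Independent Safety Review Committee (SISRC) finds unanticipated and unexpected. Section 8.5 leaves further detail to the SISRC Charter.

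A separate safeguard stands in Protocol 4.2, the synopsis and SAP 3.1. The first 6 randomized subjects are staggered by at least a week. One definitely related SAE among them brings SISRC review and a recommendation on study status. Competitive enrolment follows if there is none.

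**The concern.** A minimum sample before a rule is applied normally guards against reacting to a small denominator. Here it cannot do so, because the threshold is a count within 10 and the count cannot fall. Once the third event has occurred, the remaining subjects up to the tenth supply no information that bears on whether this rule is met. They are simply dosed while enrolment stays open.

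The delay matters only where no other trigger acts first. It could do so for a serious but non-fatal reaction that the protocol already lists as a product risk, such as hemolysis or renal failure (2.3.2), because a listed risk may not count as an unexpected signal.

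**Working it through.** The plan gives no operating characteristic for this rule, so there is no stated figure to reproduce.

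**Inputs.** Threshold 3 subjects, denominator 10 dosed, first application at 10 or more dosed (8.5). Allocation 1:1 with no block size stated (4.3.2). First 6 randomized staggered (4.2). The true rate p of the event is not given; 5% to 50% is assumed. Each event is taken to be known before the next subject is dosed.

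**Step 1, logic.** If the third affected subject is dosed subject k, with k from 3 to 9, the count at 10 is at least 3. Further subjects dosed before the rule may be applied: 10 − k, so 7 for k = 3 and 1 for k = 9.

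**Step 2, what the other numeric triggers leave uncovered before the tenth dosed subject.**

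| Trigger | Why it may not act |
|---|---|
| Related death | Event is non-fatal |
| Grade 4 in first 3 randomized; 2 same-kind Grade 4 SAEs | Event is Grade 3 or lower |
| Hypersensitivity or anaphylaxis | Another reaction type |
| 5 subjects with related Grade 3 or 4 TEAEs | Fewer than 5 so far |
| 10 subjects in one organ class | Cannot be met with 9 dosed |

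For example, 4 of the first 9 dosed could have a definitely related, same-kind, non-fatal Grade 3 SAE without meeting any numeric trigger, provided no other subject has a related Grade 3 or 4 TEAE.

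**Step 3, this rule read alone.** P(third event at dosed subject k) = C(k−1, 2) p³ (1−p)^(k−3). Summing over k = 3 to 9 gives P(at least 3 of the first 9). The mean of 10 − k is taken over the same cases.

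**Step 4, allowing for the stagger.** If d of the first 6 randomized are dosed and event-free, the third event falls at dosed subject d + 3 at the earliest, so the maximum wait is 10 − (d + 3) = 7 − d. With d = 3 this is 4. The third event must then be among dosed subjects 4 to 9, with probability P(at least 3 of 6). With j the position of the third event among those 6 (j = 3 to 6), the wait is 7 − j.

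| Assumed rate p | Rule alone: P(third event by dosed subject 9) | Mean further dosed (max 7) | 3 dosed and event-free in stagger: P(third event by dosed subject 9) | Mean further dosed (max 4) |
|---|---|---|---|---|
| 5% | 0.8% | 2.6 | 0.2% | 1.8 |
| 10% | 5.3% | 2.8 | 1.6% | 1.8 |
| 20% | 26% | 3.1 | 10% | 1.9 |
| 30% | 54% | 3.5 | 26% | 2.1 |
| 50% | 91% | 4.5 | 66% | 2.4 |

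Check at 30%, last two columns: 0.027 + 0.0567 + 0.0794 + 0.0926 = 0.256; mean wait (4×0.027 + 3×0.0567 + 2×0.0794 + 1×0.0926)/0.256 = 2.1.

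The fourth column is conditional on an event-free stagger. Multiplying by (1−p)³ gives unconditional values of 5.1%, 8.8% and 8.2% at 20%, 30% and 50%.

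**Step 5, false alarms.** P(at least 3 of 10) is 0.012, 0.070, 0.322, 0.617 and 0.945 at 5%, 10%, 20%, 30% and 50%. It is the same whether the count is acted on at the third event or at subject 10.

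**Step 6, the denominator.** The text says at least 10 and does not say whether per 10 is cumulative, rolling or by block. As a running proportion first checked at 11 dosed, 3/11 = 27% is below 30%, so three early events would not meet it. On that reading 4 events are needed at 11 to 13 dosed and 5 at 14 to 16.

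**The case against.** The strongest answer is that 8.5 should not be read alone. During the stagger the same class of event, a definitely related SAE, brings SISRC review at a count of one. Under simple 1:1 randomization the chance that none of the first 6 receives Gamunex-C is (1/2)^6 = 1.6%. So a reader who infers that up to 7 subjects would be exposed with no safeguard in play goes further than the documents allow. Seven also requires an event in every one of the first 3 dosed. If those events are all Grade 3, the 5-subject rule can end the wait sooner: 7 is then reached with probability 89%, 66%, 42% and 11% at rates of 10%, 20%, 30% and 50%. This objection stands and limits the size of the point. It does not remove it, because the stagger yields a recommendation rather than automatic suspension, and at 1:1 it covers about 3 dosed subjects.

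Three further objections stand in part:

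- **High rates are unlikely.** Protocol 2.2 describes hemolysis as isolated and thromboembolic reactions as very rare. Definitely related (8.3.4) is also a demanding category in ICU patients.
- **A listed risk may still count as unexpected.** Protocol 8.3.6 allows this if its severity or outcome departs from the reference information. The SISRC is also told of relevant SAEs within 3 days at most.
- **Reporting is not instant.** Infusions run over 4 or 5 days and enrolment becomes competitive, so some of the further subjects would be dosed before the third event was known, whatever the rule said.

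A reader might also infer that for Grade 3 or 4 events the rule protects only at 10 to 13 dosed, because the 5-subject rule has acted by the time 5 events are needed. That holds only for a running proportion. With a rolling or block denominator, three events can trigger the rule later, and the text does not settle which applies.

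**Conclusion.** The point holds in a limited form. Within the first 10 dosed, the wait cannot alter whether the sponsor's own threshold is met; it only postpones acting on it. The exposure is confined to non-fatal, definitely related, same-kind SAEs of Grade 3 or lower that fall outside the hypersensitivity rule and are not judged an unexpected signal, while fewer than 5 subjects have related Grade 3 or 4 TEAEs. It arises mainly after the stagger.

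A realistic size is about 2 further subjects, at most 4, assuming 3 of the first 6 randomized are dosed and event-free. The probabilities rest on assumed event rates and on immediate knowledge of each event. At 5% to 10% the scenario is uncommon even for the rule read alone (0.8% to 5.3%). The statement that three early events are certain to trigger the rule assumes a check at exactly 10 dosed, or a count among the first 10. The SISRC Charter may settle this but is not available here. This is an inexpensive safety clarification, not a flaw that undermines the trial's safety oversight.

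**What to change.** In Protocol 8.5:

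1. Reconcile the delay sentence with the 3-per-10 threshold, so that a threshold already met among the first 10 dosed is not held back until the tenth.
2. State how this trigger relates to the other triggers and to the review of the first 6 randomized in 4.2.
3. State whether per 10 after the tenth dosed subject is cumulative, rolling or by block.

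Keep the SISRC Charter consistent. No new clinical threshold is proposed.

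The cost is a few sentences in two documents. The downside is a possibly earlier temporary suspension pending investigation. There is no added false-alarm risk within the first 10 dosed, because the same data would meet the rule at subject 10.

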9 STATISTICS

9.1 Statistical Methods

Descriptive statistics will include the number of non-missing observations, mean, standard deviation (SD), median, minimum, and maximum values for the continuous/quantitative data or absolute and relative frequency counts and percentages for categorical/qualitative data. All statistical tests will be 2-sided at a significance level of 0.05.

An interim analysis will be conducted after 50 subjects (approximately 25 per group) for safety variables through Day 29. Due to the exploratory nature of this phase 2 study, the multiplicity adjustments will not be considered; full details will be described in the statistical analysis plan. This interim evaluation simply represents Sponsor safety due diligence.

There will be 3 analysis populations in this study; 2 populations for efficacy assessments and 1 population for safety evaluation.

The intention to treat (ITT) population is defined as all subjects who are randomized. The ITT population will be used for all efficacy analyses.

The Per-Protocol (PP) population is defined as the subset of subjects included in the ITT population who do not present major protocol violations which might have an impact on the primary efficacy endpoint, and complete at least 80% of the IP. The primary efficacy analyses will be carried out using the PP population if different from the ITT population.

The Safety population is defined as the subset of subjects who receive at least any amount of IVIG plus SMT or SMT alone. Safety analyses will be based on the Safety population.

The primary efficacy analysis will be carried out on the ITT population and repeated on the PP population (if different from the ITT population) by Fisher's exact test or Chi-square test. Secondary and exploratory efficacy analyses will be analyzed by means of Kaplan-Meier survival estimates and curves and compared between treatment groups by means of the Log-rank test for time to event variables, analysis of covariance (ANCOVA) or Student's t test for normally-distributed variables or Wilcoxon rank-sum test for non-normally-distributed variables. Detailed data handling and evaluation procedures and details of the interim reviews will be described in the Statistical Analysis Plan (SAP). The SAP may include exploratory analyses of various aspects of SMT inclusive of different interventional strategies and evolving treatment modalities.

Grifols will analyze use of COVID-19 specific, potentially disease modifying treatments between arms and this will be fully detailed in the SAP since medical understanding of COVID-19 interventions is rapidly evolving and for ethical reasons (apart from participation

GRIFOLS Bioscience Industrial Group	Number	BlG-CL-PPR-000020	Version	4.0	Status	Effective	Effective Date	19-Jul-2021	Page	64 of 91
	GC2007 - A Multicenter, Randomized, Open-label Parallel Group Pilot Study to Evaluate Safety and Efficacy of High Dose Intravenous Immune Globulin (IVIG) plus Standard Medical Treatment (SMT) versus SMT alone in									

in another clinical trial) there are no restrictions on what are perceived to be potentially life-saving therapies. Additionally, a sensitivity analysis evaluating potential effects of fluid balance will be included in the SAP.

